## 5.6. Rehabilitation therapy

Standard care for children with CP involves the provision of rehabilitation therapies. It has also been hypothesised that stem cell-induced neuroplasticity might be optimised under “enriched” conditions, i.e. in the presence of activity-dependent plasticity arising from active rehabilitation based on neuroscience principles [58]. For both ethical and scientific reasons, all participants enrolled within this study will continue to receive their standard rehabilitation treatments. The study will request a monthly home diary of the family-determined therapy regimen for the duration of the trial.

## 6. STUDY VISITS AND PROCEDURES SCHEDULE

Study phase	Enrolment	Baseline	Infusion	Follow up					
Visit number	1	2	3	4	5	6	7	8	9
Timing	> 8 wks prior to infusion	21 days prior to infusion	0	1 day	1 wk	1 mo	3 mo	6 mo	12 mo
Tolerance	Any time	> 3 wks since Visit 1	- Within 10-30 days of clear virology screen - CBU available	± 0 days	±2 days	± 7 days	± 2 wks	± 2 wks	± 2 wks
Location	Hospital	Hospital	Hospital	Hospital	Hospital, home	Hospital	Hospital	Hospital, community	Hospital
Informed consent (45 mins)	X								
CP assessment (30 mins)		X							
Medical history (0.5 hr)		X							
Physical examination (0.5 hr)		X	X	X		X	X	X	X
Medical assessment (10 mins)				X	X	weekly	X	X	X
Assessment of motor function (45 mins)		X					X		X
Assessment of upper limbs (15 mins)		X					X		X
Assessment of quality of life (0.5 hr)		X					X		X
Assessment of cognition (2hr 15)		X							X
Infusion of UCB (30 mins)			X						
Intravenous fluids, observation (6 hrs)			X						
Anti-D administration if required (5 mins)				X					
Blood collection	X	X	2X	X	X	X	X		
Rehabilitation Therapy									
Length of visit	1 hr	6 hrs (may need two visits)	9 hrs	1 hr	1 hr	1 hr	2 hrs	1 hr	4 hrs

## 7. CLINICAL AND LABORATORY ASSESSMENTS – METHODOLOGY

### 7.1. Safety measures

#### Medical History

A medical history will be taken at visit 2, and permission to access hospital medical records is requested.

A questionnaire will be used to gather information on immunological health status.

#### Physical examination

Physical examinations will be conducted by both a paediatrician and a transplant specialist prior to infusion. They will examine the participant to confirm eligibility by confirming the CP diagnosis during visit 2, and to ensure they are healthy. Participant weight and height will be measured and BMI calculated, the doctor will listen to the heart and lungs, feel the abdomen, take pulse and respiratory rates and confirm the neurological signs including assessing muscle tone and reflexes.

After infusion, a transplant specialist will physically examine each participant at visits 4, 6, 7 and 8 (1 day, 1, 3 and 12 months post-infusion) as part of the medical assessment, to look for subtle signs of GvHD that may not be picked up by participant carers.

#### Medical assessment

Medical assessment will be conducted at 1 day, weekly until 1, 3 and 12 months after infusion, and at any time that the participant or their family feel concerned. All medical assessments will be conducted by a transplant specialist. It comprises a short list of questions of participant safety over the phone from the trial doctor, focused on signs of infection and inflammation. Should the participant show any indication of needing more detailed examination, they will be asked to return to the infusion hospital as soon as possible. If necessary, they may of course attend their nearest medical service and the trial doctor will follow this up.

At visit 6 (6 months post infusion), a paediatrician either at a trial site hospital or in the local community will conduct a general health assessment of the participant.

#### Observation

Vital signs will be monitored by the nurse prior to UCBC infusion, during the infusion, every 15 minutes for 1 hour, then every 30 minutes for 2 hours. The monitoring will include temperature measurement (in °C), blood pressure (in mmHg), pulse oximetry (in % oxygen saturation) and checks for nausea and discomfort.

Participants will also be monitored for symptoms of toxicity, including nausea, fever, chills, and for symptoms of anaphylaxis including wheezing and urticaria.

A transplant physician will be available and called if vital signs fall outside the normal range (see section 8) or if there are signs of an adverse event.

#### Assessment of CBU

Cord blood is assessed initially upon donation prior to cryopreservation, including a maternal health follow up. While preparing to release a CBU, the CBB will undertake a reference thaw of a pilot sample to predict post-thaw characteristics, and a pilot sample will also be sent to the Red Cross Transplantation Service for HLA typing. If the CBU meets quality and release criteria of the CBB and fits eligibility requirements at this point, it will be transported to the cell therapy lab at the infusion hospital.

The cell therapy lab of each infusion hospital will examine the CBU for release. If the CBU passes inspection again, the infusion date will be confirmed. On the day of infusion, the CBU will be thawed and washed and samples taken to assess for TNC, CD34+ cell count and viability, aerobic and anaerobic sterility, and supernatant haemoglobin although results from these assays are not available until a day or more after infusion. This follows standard operating procedure in preparation for haemopoietic stem cell

(HSC) transplant and hence focuses on HSCs. This is useful information and will form part of the study report; however UCBC therapy for CP has quite different aims to a HSC transplant.

Therefore, the private cord blood bank labs will also conduct assessments of UCBCs with a focus on other cell types and potential modes of activity. Immunophenotyping will examine the range of cells present; and monocyte activity will be examined.

#### Analysis of blood – pre-transplant work up

Blood samples taken within 3 weeks of infusion will be used to assess general health and eligibility for infusion. A full blood examination, blood group and antibody testing, urea, electrolyte and liver function tests, C-reactive protein assay and virology screen will be undertaken.

#### Analysis of blood – immunology screen

The immunology screen involves full blood examination, immunoglobulin levels, lymphocyte subsets and naïve T-cells (or the local laboratory's equivalent test) performed at the local hospital's diagnostic laboratory. Local diagnostic laboratories' reference ranges will be used to interpret results in conjunction with the participant's clinical history and responses to the immunology health screening questionnaire.

#### Analysis of blood – studying infusion safety and mechanism

Blood samples taken immediately before, 4 hours, 24 hours, 1 week, 1 month and 3 months after infusion will be used to collect serum, DNA and RNA.

The sample taken prior to infusion will be used as both a baseline for any changes after infusion, as well as a control sample to compare with each participant's CBU.

The samples taken up until 1 week post infusion will have a full blood examination, urea, electrolyte and liver function tests, C-reactive protein assay and lymphocyte subsets assay. Chimerism will be assessed using a new digital PCR method to detect copy number deletions (CNDs) which is more sensitive and accurate than current standard chimerism assays (sensitivity to 50 genome equivalents/mL). This assay will be centralised to MCRI Cyto-molecular Diagnostics Lab as it is not generally available, and therefore requires sample transport. These assays are for safety, and to examine longevity of infused sibling cells in the circulation.

This study will also gather information on the activity of infused cells. The focus will be on immunophenotyping, to look at populations of classically (M1) or alternatively (M2) activated macrophages, Treg cells and other immune cells, since this is one of the primary modes of UCBC action.

The samples taken at 1 and 3 months after infusion will be used for C-reactive protein assay and lymphocyte subsets assay. These are to examine longevity of infused cells, and for safety studies to determine whether infused cells have engrafted, whether chimerism can be detected from participants receiving matched sibling UCBCs, and include assays for inflammatory markers. These tests will monitor and determine the risk of GvHD for the participants. If chimerism is still detected at 3 months, further testing may be needed.

A portion of the samples will be stored at -80°C for future studies. This is important, as we expect a far greater understanding of the activity of UCBCs in cerebral palsy to emerge over the coming years which would guide future research.

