### 4. STUDY DESIGN

This is a multi-site safety study.

Sibling donor UCBCs require careful DNA testing to ensure matching with the recipient (participant). Only about 25% of siblings have full-matched blood, the 75% that are not full-matched will be excluded. No immunosuppression will be used, as the infused cells do not need to survive for long periods within the recipient and immunosuppression increases the safety risk. The first six enrolled participants to receive infusions will be GMFCS IV or V; participants with mild or moderate CP (GMFCS I, II or III) will be waitlisted. This is because the safety profile of matched sibling UCBC infusion for children with CP is unknown, we feel it is more ethical to initially trial in the participants with severe CP and gather information for interim Data Safety Monitoring Committee (DSMC) review, before continuing the trial with less impaired participants. The DSMC will review safety data from the first three participants after three months post-infusion and decide whether the trial can progress to the next three participants. After these initial six participant infusions, the DSMC will decide whether the trial can progress to infusions of participants with mild CP or not. The DSMC will provide a report to the Trial Steering Committee, who will provide the report directly to the RCH HREC for review. The HREC will make a final decision about whether the trial can expand to include children with mild or moderate CP at this point, or whether the trial will remain restricted to children with severe CP only.

[figure not shown]

Figure 1: Participant timelines for the study

Figure 2: Recruitment decision making process (next page)

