#### 4.3. Primary and secondary outcome measures

The primary objective of this study is to collect initial safety data during and after infusion of sibling UCBCs. The following outcomes will be collected to assess this objective which will be assessed at three time points:

- 1) During the infusion and up to 36 hours after
  - Clinical assessment, including vital signs and pulse oximetry
  - Laboratory assessment looking for markers of infection

- Occurrence of AEs and SAEs
- 2) Within the three months after infusion
  - Clinical assessment
  - Laboratory assessment looking for markers of immune reaction
  - Deterioration of motor function as assessed by Gross Motor Function Measure
  - Occurrence of AEs and SAEs
- 3) Within the 12 months after infusion
  - Clinical assessment
  - Deterioration of motor or cognitive function as assessed by the appropriate tool (see section 7.3)
  - Occurrence of AEs and SAEs

The secondary outcomes include:

- Efficacy of the intervention at 3 months measured by therapists on a suite of standardised psychometrically sound measures of movement, cognition and quality of life. This will be assessed in an exploratory fashion only. The areas for assessment were selected to focus on motor outcomes because CP is a primarily motor disorder; on cognitive outcomes that have shown change in an international trial [49] and anecdotally from private stem cell clinics (changes in wakefulness, attentiveness and alertness have been described); and how these might affect the participant's life; The motor and quality of life outcomes will also be measured at 3 months. Cognition will be measured at 12 months after infusion and used to calculate change from baseline. Again, the analysis of the 12 month data will be exploratory in nature.
- Understanding the longevity of infused cells. This will be achieved using chimerism studies (engraftment analysis), looking for infused cells circulating in a sibling recipient's blood. We will study chimerism by extracting circulating cell free DNA from plasma and using a new quantitative PCR method detecting differences in copy number deletions between the recipient and donor. It will be reported as the fraction of donor DNA in the sample at each time point for each individual, and constitutes both a safety and mechanistic study.

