**Table 1: Details of all proposed blood samples**

Blood collection	Volume	When is it taken?	What is it for?	Where does it go?	What happens to it afterwards?
1	9 mL; Blood spot	Soon after enrolment	- Low resolution HLA typing to match sibling or autologous CBU with participant - Immunology screening	- Red Cross Transplantation Services - RCH Melbourne Immunology Lab*	Transported, destroyed

Sibling sample	2.7 mL	Soon after enrolment (only if assay cannot be conducted on CBU)	- To assess blood group and rhesus type	- Infusion hospital labs	Transported, destroyed
Maternal sample	2.7 mL	3 weeks prior to infusion (if not previously conducted)	- To assess HepBcAb (to assess risk of HepB contamination of cord blood)	- Infusion hospital labs	Transported, destroyed
2	9 mL 7 mL	3 weeks prior to infusion	- Low resolution confirmatory HLA typing to ensure matching blood is used - To assess blood group and rhesus type - To assess health of participant	- Red Cross Transplantation Services - Infusion hospital labs	Transported, destroyed
3	4 mL 7.2 mL	2 hours before infusion	- To compare with the blood sample taken after treatment	- Cell therapy lab - Infusion hospital labs - Cyto-molecular diagnostics lab* - Research labs*	Frozen, transported and stored
4	8.2 mL	4 hours after infusion	- To look for inflammation - To compare with blood taken at baseline	- Infusion hospital labs - Cyto-molecular diagnostics lab* - Research labs*	Frozen, transported and stored
5	8.2 mL	24 hours after infusion	- To check for infection - To check the cell types in the participant's blood	- Infusion hospital labs - Cyto-molecular diagnostics lab* - Research labs*	Frozen, transported and stored
6	8.2 mL	1 week after	- To look for inflammatory markers, signs of GvHD - To check the cell types in the participant's blood	- Infusion hospital labs - Cyto-molecular diagnostics lab* - Research labs*	Frozen, transported and stored
7	6.4 mL	1 month after	- To check the cell types in the participant's blood, chimerism assessment - To look for inflammatory markers, signs of GvHD	- Infusion hospital labs - Cyto-molecular diagnostics lab* - Research labs*	Frozen, transported and stored
8	6.4 mL	3 months after	- To check the cell types in the participant's blood, chimerism assessment - To look for inflammatory markers, signs of GvHD	- Infusion hospital labs - Cyto-molecular diagnostics lab* - Research labs*	Frozen, transported and stored

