#### *Serious Adverse Event Reporting*

Should an AE be categorised as serious, the local HREC will be notified within 72 hours of its occurrence using Appendix 12: Serious adverse event report form. The HREC safety reporting form will be completed, signed and submitted by the coordinating principal investigator with the trial coordinator. Should there be a SUSAR, HREC will be notified within 72 hours as with a SAE. All SUSARs occurring in a study participant will be reported to the Therapeutic Goods Administration (TGA) within 2 weeks of first occurrence. The report will be completed, signed and submitted by the coordinating principal investigator with the trial coordinator.

Graft-versus-Host Disease (GvHD) of Grade II or above (as defined in Appendix 13:) will stop the trial. The DSMC may advise stopping the trial if other SAEs occur, based on clinical discussion of the SAE and its potential relationship to the study treatment.

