## **9. STATISTICAL METHODS**

As the primary aim of this study is to assess safety, the sample size of 12 participants was selected to allow sequential groups of three participants, followed by another three participants, followed by the final six participants. Although we do not expect the cell content of cord blood units to affect safety, and hence a dose escalation safety structure is not required, cell content may relate to the efficacy of the infusion and will be analysed at the conclusion of the study.

While we do not expect the participants to be representative of the general population with CP, we will compare group characteristics with population data from the Australian Cerebral Palsy Register to assess the generalisability of the results obtained. Given the pilot nature of this trial the results from this study will be presented descriptively only. Safety data will be summarised as the proportion of participants who have an SAE and an AE within either of the three safety time periods: within 36 hours, within three months or within the 12 month study period. The change in lab results at each time point will be presented relative to baseline. We will summarise the feasibility data through a summary of the number and proportion of patients recruited of those who were contacted the study team, and a breakdown of the reasons for non-participation. The number of withdrawals and reasons for withdrawal and the number of protocol violations and deviations will also be presented. Change in motor and cognitive function will be presented relative to baseline. Donor cell longevity data will only be presented for the participants receiving sibling UCBC infusions, and categorised as 'immediate rejection' to indicate return to baseline fraction of foreign cell-free

DNA within 24 hours; 'rejection' to indicate return to baseline fraction of foreign cell-free DNA by 1 month; 'slow rejection' to indicate the presence of between 200 donor genome equivalent/ml and engraftment at 3 months, and 'engraftment'.

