
Hypertension Definition: A disorder characterized by a pathological increase in blood pressure; a repeatedly elevation in the blood pressure exceeding 140 over 90 mm Hg.
	
 
• During or immediately after infusion
 
• Within 36 hours of infusion
 
	Prehypertension (systolic BP 120 - 139 mm Hg or diastolic BP 80 - 89 mm Hg)	Stage 1 hypertension BP >ULN medical intervention indicated; recurrent or persistent (≥24hrs)	Stage 2 hypertension (systolic BP ≥160 mm Hg or diastolic BP ≥100 mm Hg); medical intervention indicated; more than one drug or more intensive therapy	Life-threatening consequences (e.g., malignant hypertension, transient or permanent neurologic deficit, hypertensive crisis);	Death

				than previously used indicated	urgent intervention indicated	
Hypotension Definition: A disorder characterized by a blood pressure that is below the normal expected for an individual in a given environment.	
 
• During or immediately after infusion
 
• Within 36 hours of infusion
 
	Asymptomatic, intervention not indicated	Non-urgent medical intervention indicated	Medical intervention or hospitalization indicated	Life-threatening and urgent intervention indicated	Death

Graft versus Host Disease [63]

Stage	Skin	Liver (bilirubin)	Gut (stool output per day)
0	No GVHD rash	< 2mg/dl	Child: < 10 ml/kg/day or persistent nausea
1	Maculopapular rash 25% BSA	2–3 mg/dl	Child: 10–19.9 ml/kg/day or persistent nausea, vomiting or anorexia, with a positive upper GI biopsy
2	Maculopapular rash 25–50% BSA	3.1–6 mg/dl	Child: 20–30 ml/kg/day
3	Maculopapular rash > 50% BSA	6.1–15mg/dl	Child: > 30 ml/kg/day
4	Generalized erythroderma plus bullous formation	> 15mg/dl	Severe abdominal pain with or without ileus
Grade			
I	Stages 1–2	None	None
II	Stage 3 or	Stage 1 or	Stage 1
III	—	Stages 2–3 or	Stages 2–4
IV	Stage 4 or	Stage 4	—

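### Bilirubin alone can take GvHD to the grade that stops the trial, yet no liver test is named for the 1- and 3-month samples used to look for GvHD

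*Protocol*

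**What the plan says.** - **Stopping rule (Section 8, Serious Adverse Event Reporting):** "Graft-versus-Host Disease (GvHD) of Grade II or above (as defined in Appendix 13:) will stop the trial". For any other serious event the monitoring committee (DSMC) may advise stopping, so this is the only automatic rule.
- **Grading (Appendix 13, GvHD table):** the liver is staged on bilirubin and nothing else. Grade II is reached by skin stage 3, or liver stage 1, or gut stage 1.
- **Tests to 1 week (Section 7.1, Analysis of blood – studying infusion safety and mechanism):** "The samples taken up until 1 week post infusion will have a full blood examination, urea, electrolyte and liver function tests", together with C-reactive protein and lymphocyte subsets.
- **Tests at 1 and 3 months (same section):** "The samples taken at 1 and 3 months after infusion will be used for C-reactive protein assay and lymphocyte subsets assay". The text adds chimerism and inflammatory markers, and states that these tests are meant to monitor and determine GvHD risk. It names no liver test.
- **Purpose of the samples (Table 1):** samples 6, 7 and 8 (1 week, 1 month, 3 months) share the entry "To look for inflammatory markers, signs of GvHD".
- **Use of the data:** Section 4.3 lists, within three months, "Laboratory assessment looking for markers of immune reaction". Section 9 says "The change in lab results at each time point will be presented relative to baseline". Section 4 says "The DSMC will review safety data from the first three participants after three months post-infusion and decide whether the trial can progress". Section 1.3 places the first review at one month instead.

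**The concern.** A stopping rule is only as good as the measurements behind it. Here one of the three organ criteria is a laboratory value, and the panel listed for the two later samples does not contain it. A site that ran exactly the assays in Section 7.1 would have no bilirubin at 1 or 3 months, although Table 1 says those samples are taken partly to look for GvHD.

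These two samples are the laboratory data nearest to the decision to infuse the next children. The DSMC could therefore clear the next group with the liver criterion last measured at 1 week. The planned summary of laboratory change from baseline would also have no liver value at either time point, although a baseline liver test is part of the pre-infusion work-up.

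**Working it through.** The protocol states no figure to reproduce. The check applies the grading table and then compares the assays named at each sample.

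**1. Does the liver criterion suffice by itself?** Take a child judged to have GvHD with skin stage 0, gut stage 0 and bilirubin 2–3 mg/dl (liver stage 1). Appendix 13 gives Grade II, and Section 8 stops the trial. Liver stages 2–3 give Grade III and stage 4 gives Grade IV.

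**2. How many routes to Grade II or above need bilirubin?**

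| Grade | Skin | Liver | Gut |
|---|---|---|---|
| II | stage 3 | stage 1 | stage 1 |
| III | – | stages 2–3 | stages 2–4 |
| IV | stage 4 | stage 4 | – |

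That is 2 skin + 3 liver + 2 gut = 7 routes, of which 3 need bilirubin.

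**3. Where is a liver test named?** (Section 7.1 and Table 1)

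| Sample | Time after infusion | Volume | Liver function tests named |
|---|---|---|---|
| 4 | 4 hours | 8.2 mL | yes |
| 5 | 24 hours | 8.2 mL | yes |
| 6 | 1 week | 8.2 mL | yes |
| 7 | 1 month | 6.4 mL | no |
| 8 | 3 months | 6.4 mL | no |

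Liver tests are named at 3 of 5 samples and not at 2. Across the trial that is 2 × 12 = 24 draws. For the first six children, whose data feed the planned gates, it is 2 × 6 = 12. The visit schedule in Section 6 lists only blood collection, and no other section adds a liver test after 1 week.

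**4. How old is the last named liver test at each review point?** Take 1 month as 30 days and 3 months as 91 days. The Section 6 tolerances are ±2 days at 1 week, ±7 days at 1 month and ±14 days at 3 months.

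- 1 week: day 7 (range 5 to 9)
- 1 month: day 30 (range 23 to 37). Gap 30 − 7 = 23 days; range 23 − 9 = 14 to 37 − 5 = 32 days
- 3 months: day 91 (range 77 to 105). Gap 91 − 7 = 84 days; range 77 − 9 = 68 to 105 − 5 = 100 days

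**5. What else is scheduled in that gap?** The transplant physician's weekly assessments run to 1 month. A transplant specialist examines the child at 1 and 3 months, and families can ask for an assessment at any time. Between 1 and 3 months nothing else is scheduled. None of these steps includes a bilirubin measurement unless someone orders one.

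**The case against.** **A raised bilirubin is not GvHD.** The rule stops the trial for GvHD of a given grade, so the diagnosis comes first. That stands: bilirubin alone settles the grade, not the diagnosis. But a liver-only case cannot be suspected or graded from a value that nobody measured.

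**The list may not be closed.** Table 1 describes samples 6, 7 and 8 in the same words, and sample 6 does get liver tests, so those words could be meant to cover them at 1 and 3 months. Samples 7 and 8 also go to the infusion hospital laboratories. Nothing in the text forbids the test, so this has some force. Against it, Section 7.1 sets out two different panels, and the drop from 8.2 to 6.4 mL fits a smaller one. A multi-site trial should not depend on the generous reading.

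**Chimerism is the chosen monitor.** The protocol tracks donor cells as a marker of GvHD risk and allows for further testing if they persist at 3 months. That is a reasonable risk marker, but it shows whether donor cells remain and does not stage the liver. The follow-up is also discretionary.

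**The outcome sections are not contradicted.** C-reactive protein, lymphocyte subsets and inflammatory markers can serve as markers of immune reaction, and Section 9 can be read as covering whichever tests were done. Both points are fair. The consequence there is a missing liver value, not a breach of either section.

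**The remaining gap is narrow.** Clinical review would pick up skin and gut disease and visible jaundice. This stands and limits the size of the point.

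**Conclusion.** The concern holds. If the named panel is followed, the liver arm of the only automatic stopping rule goes unmeasured at both later scheduled samples. The last named liver test is then about 23 days old (14 to 32) at 1 month and about 84 days old (68 to 100) at 3 months.

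The exposure is limited to liver-only GvHD of Grade II or above without clinical signs. The protocol gives no frequency for this, and none is claimed. The count of 3 routes in 7 describes the grading table and is not a probability.

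The conclusion rests on three assumptions: that liver function tests include bilirubin, which the protocol does not say; that sites run the assays named and no more; and that months are 30 and 91 days. Sections 1.3 and 4 differ on whether the first review is at one or three months, but the gap exists on either reading. It should be corrected, because it concerns the primary safety objective and the remedy is small.

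**What to change.** In Section 7.1 and in Table 1, name liver function tests including bilirubin for sample 7 (1 month) and sample 8 (3 months). Naming bilirubin removes any doubt about what the local panel contains, and makes the liver criterion available at both samples that inform DSMC review.

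The cost is one routine assay on two draws that are already taken and already sent to the infusion hospital laboratories. If the volume returns to that of samples 4 to 6, the increase is 8.2 − 6.4 = 1.8 mL per draw, or 2 × 1.8 = 3.6 mL per child. No visit is added.
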